15.3.2.1 Efficacy/ADA Correlation Analysis

Summary tables will present ACR20 and ACR50 by ADA status. A line graph will also be provided to display the ACR20 response rate over time by treatment arm and ADA status.

Boxplots displaying *DAS28-ESR* change from baseline at Week 12 by both ADA status and lower and upper quartiles of ADA titers will be produced. The change from baseline for *DAS28-ESR* will be the value for the specified visit, the ADA status or ADA titers will be the values for the treatment period.

The ADA titer quartiles will be defined using the highest ADA titer value from each subject for the period from baseline to Week 12 where subjects with ADA negative for the whole period will be assigned to a titer value of 0. ADA titers will be computed by splitting the subjects by treatment arm, taking their highest ADA titer values for the treatment period, arranging the values from smallest to largest and splitting into quartiles.

Line graphs will also be provided to display the change from baseline over time for continuous efficacy endpoints (TJC28, SJC28, ESR, DAS28-ESR, CDAI, SDAI), split by treatment arm and ADA status at a specified visit.

In addition, scatterplots of percentage change from baseline in continuous efficacy endpoints (DAS28-ESR, CDAI, SDAI) vs titer on log2 scale (if appropriate) will be generated for each treatment with separate symbols (if appropriate) for each study week.

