Exploratory objective

The exploratory objective is to evaluate population pharmacokinetics (PK) of MSB11022-CCI and Humira in patients with moderately to severely active RA

Methodology: This trial is a two-arm, randomized, multicenter, double-blind, parallel group trial designed to compare the safety, immunogenicity, and efficacy of MSB11022-ccl with Humira in approximately 260 randomized patients with moderately to severely active RA during a 52 week period.

Baseline is defined as the day on which the first dose of the investigational medicinal product (IMP) (blinded study drug) is administered (Week 0). The trial will include a pre-trial evaluation period (screening period, from 28 days to 3 days prior to drug administration), a double-blind 48-week treatment period, a 4-week safety follow-up visit, and a 4-month safety evaluation period. The primary safety endpoint will be assessed up to Week 52, key secondary efficacy endpoint will be assessed at Week 12.

Re-screening will be allowed once for those patients who do not meet the inclusion/exclusion criteria within the above specified time limits. The Medical Monitor must promptly inform the Sponsor about requests and reasons for re-screening. An IDMC will review the safety data from this trial on an ongoing basis.

Eligible patients will be randomized in permuted blocks in a 1:1 ratio by an interactive web response system (IWRS) to receive either MSB11022-CCI subcutaneous (sc) or Humira sc at a dose of 40 mg every other week starting at baseline up to and including Week 48. Randomization will be stratified by the type of systemic therapy previously received: non-biological (biologic naïve patients) versus biological (biologic experienced patients). Patients who previously received both (biological and non-biological systemic therapies) will be assigned to the "biological" group. The exposure to previous biological agents will be limited to one tumor necrosis factor (TNF) inhibitor other than adalimumab. The

MSB11022 in Moderate to Severe Rheumatoid Arthritis version 3.0 Final

participation of patients in the previous biological systemic therapy stratum will be capped at 20% of the total number of patients randomized. Capping will be enforced through application of an IWRS.

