15.3.2 Immunogenicity Analysis

Immunogenicity data will be summarized by treatment arm for the SAF analysis set. Overall ADA status (negative or positive, where positive is defined as at least one positive result post-dose) will be summarized as well as ADA titers and presence or absence of neutralizing antibodies.

Time to positive ADA status, calculated from Trial Day 1, will also be analyzed. Subjects who discontinued the study or were lost to follow-up, or had not reached the endpoint of interest at the time of analysis, will be censored at the date of last sample collection. Results will be summarized by means of Kaplan-Meier curves together with a summary of associated statistics (median, 95% confidence interval) and the number of subjects under risk.

Summary statistics will be presented for the actual titer values, by treatment arm and visit up to Week 52. Boxplots will be produced to present the ADA titer results graphically. The boxplots will present Q1, Q3, median, minimum and maximum.

The number and percentage of ADA positive and NAb positive subjects will be presented for each visit up to Week 52.

The analysis exploring the correlation between ADA and efficacy, PK and safety will be described in Sections 15.3.2.1, 15.3.3.1, and 16.6 respectively.

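### SAP 15.3.2.1 gives conflicting ADA windows for the Week 12 DAS28-ESR boxplots, and read literally lets antibodies first found after Week 12 classify a Week 12 outcome

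*SAP*

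**What the plan says.** SAP 15.3.2.1 (Efficacy/ADA Correlation Analysis) plans boxplots of DAS28-ESR "change from baseline at Week 12 by both ADA status and lower and upper quartiles of ADA titers will be produced". The outcome is the value at the specified visit, whereas "the ADA status or ADA titers will be the values for the treatment period". The next paragraph gives two rules for the titer quartiles:

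- They are defined "using the highest ADA titer value from each subject for the period from baseline to Week 12", and "subjects with ADA negative for the whole period will be assigned to a titer value of 0".
- They are computed within each arm by "taking their highest ADA titer values for the treatment period, arranging the values from smallest to largest and splitting into quartiles".

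SAP Section 6 describes "a double-blind 48-week treatment period, a 4-week safety follow-up visit, and a 4-month safety evaluation period". SAP 15.3.2 sets the default for ADA status: "positive is defined as at least one positive result post-dose". It names no last visit.

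For the ACR endpoints, 15.3.2.1 says only "Summary tables will present ACR20 and ACR50 by ADA status". It adds a line graph of the ACR20 rate over time by arm and ADA status. Neither output has an ADA window. The line graphs of continuous endpoints differ: they use ADA status at a specified visit, although that visit is not named.

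**The concern.** A Week 12 outcome should be related to antibodies present by Week 12. The status sentence, taken with the any-positive definition, lets a sample from Week 24 or Week 36 decide the group in which a Week 12 result is shown. That reverses the time order.

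The quartile paragraph adds a direct conflict. A patient negative through Week 12 and positive at Week 24 has titer 0 under the first rule, and may be in the top quartile of the arm under the second. Two programmers following the same SAP could produce different figures.

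Protocol 5.2.1 says the data should allow exploration of immunogenicity against efficacy, including reduced or lost response. If later converters still respond like negatives at Week 12, mixing them into the positive group would make that relation look weaker than it is.

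**Working it through.** **Step 1: the windows side by side (SAP 15.3.2 and 15.3.2.1).**

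| Output | ADA window stated |
|---|---|
| DAS28-ESR boxplots at Week 12, by status | Treatment period |
| Same boxplots, titer quartiles, first sentence | Baseline to Week 12 |
| Same boxplots, titer quartiles, second sentence | Treatment period |
| ACR20/ACR50 tables; ACR20 line graph | None, so the any-positive default would apply |
| Continuous-endpoint line graphs | Status at a specified (unnamed) visit |

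The inconsistency needs no arithmetic.

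**Step 2: how much the window could matter.** The plan gives no figure to reproduce: it states neither ADA incidence by visit nor an effect of ADA on response. The inputs below are therefore assumptions, shown as ranges.

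- d: true Week 12 difference between patients positive by Week 12 and never-positive patients. For scale, 0.6 DAS28 units, which Protocol 5.2.3.3 says may already be clinically meaningful.
- E: share of patients ever positive, 0.3 to 0.8.
- f: share of ever-positives already positive by Week 12, 0.5 to 0.9.
- g: share of d already present at Week 12 in those who convert later, 0 to 1.
- h = E(1 − f)/(1 − Ef): share of later converters among those still negative at Week 12.

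Difference shown by the whole-period split: d × [f + (1 − f)g].

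Difference shown by the up-to-Week-12 split: d × (1 − hg).

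**Step 3: later converters respond like negatives at Week 12 (g = 0).** The whole-period split shows d × f and the Week 12 split shows all of d.

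| f | Shown | Lost | If d = 0.6 |
|---|---|---|---|
| 0.5 | 50% | 50% | 0.30 |
| 0.7 | 70% | 30% | 0.42 |
| 0.9 | 90% | 10% | 0.54 |

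**Step 4: later converters are already fully affected (g = 1).** The whole-period split shows f + (1 − f) = 100% of d. The Week 12 split shows 1 − h. For example, with E = 0.3 and f = 0.5, h = 0.15/0.85 = 0.18, so 82% is shown.

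| E | f = 0.5 | f = 0.7 | f = 0.9 |
|---|---|---|---|
| 0.3 | 82% | 89% | 96% |
| 0.5 | 67% | 77% | 91% |
| 0.8 | 33% | 45% | 71% |

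**Step 5: break-even.** Setting the two expressions equal gives g = (1 − f)/[(1 − f) + h]. Over f = 0.5 to 0.9 this is 0.74 to 0.71 for E = 0.3, 0.60 to 0.52 for E = 0.5, and 0.43 to 0.26 for E = 0.8. Below these values the whole-period split shows the smaller difference; above them the Week 12 split does.

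**The case against.** The best defence is that treatment period in 15.3.2.1 is loose wording for baseline to Week 12, the window named in the next paragraph. If so, no later result is used. That is possible, but the SAP does not say it, and the sentence after the Week 12 definition returns to the treatment period. The contradiction stands on either reading.

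It can also be said that other displays already use visit-level ADA results: positivity counts by visit and time to ADA (15.3.2), and scatterplots by study week (15.3.2.1). This limits the harm but does not repair the boxplots.

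Four stronger readings are tempting, and the documents do not support them.

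- *All Week 12 efficacy is split by whole-period status.* The rule is explicit only for the DAS28-ESR boxplots. For the ACR outputs the window is missing, and the continuous-endpoint line graphs use status at a visit.
- *Responders give more samples because non-responders stop at Week 24, so the relation could even reverse.* Those patients stop study drug, but Protocol 5.2 and 5.4.2 keep them in immunogenicity follow-up. The SAP Section 8 cut-off for early terminators is theoretical Week 52 or the 4-month visit, whichever is first. For a Week 24 stopper that is about Weeks 39-41, so a Week 36 sample can still count. The SAP does not say whether off-drug samples belong to the treatment period, so some imbalance is possible, but nothing shows that it is large or reverses the relation.
- *More than half of the effect is lost.* Suppose 15% are positive by Week 12 and 35% ever, with Week 12 ACR20 of 40% in positives and 60% in negatives. If later converters respond like negatives, positives show (15 × 40 + 20 × 60)/35 = 51.4%, so a 20-point gap appears as 8.6. If later converters are already at 40%, the whole-period split shows all 20 points, and the Week 12 split shows 20 × (1 − 20/85) = 15.3. One assumed scenario cannot be cited as the size.
- *The comparison of MSB11022 with Humira is distorted.* Nothing in the documents shows an effect that differs between arms.

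**Conclusion.** The point holds as an internal inconsistency with a possible, unquantified bias. For the Week 12 boxplots, the SAP sets a whole-period window for ADA status and two incompatible windows for the titer quartiles; followed literally, it classifies a Week 12 outcome by later antibodies.

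The loss is 10-50% of the true difference if later converters are unaffected at Week 12 and f is 0.5 to 0.9. It is zero if they are fully affected, in which case the Week 12 split shows the smaller difference. The case for the Week 12 window is therefore time order and reproducibility, not that it always shows the larger difference.

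The consequence is limited. These are descriptive displays, and Protocol 8.5.3.5 makes the titer-quartile correlations optional and exploratory. The primary endpoint and the between-arm ACR20 comparison do not depend on them. The wording should still be corrected, because the outputs cannot be produced unambiguously as written.

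**What to change.** In SAP 15.3.2.1:

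1. For the Week 12 DAS28-ESR boxplots, define ADA status and highest titer from post-dose samples up to and including Week 12. Delete or correct the treatment-period wording in both the status sentence and the second quartile sentence.
2. Name the visits for the ACR20/ACR50 tables, and use the same up-to-visit window for them and for the ACR20 line graph.
3. Keep the whole-period (ever-positive) split as a sensitivity display, and as the main split for Week 52. Showing both at Week 12 also lets a reader see how far later converters matter, which the documents cannot settle in advance.

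The cost is SAP wording and a date limit in the programs. No new data are needed, because ADA results by visit are already collected and reported up to Week 52. The drawback is fewer ADA-positive patients at early visits, so those groups will be described less precisely.

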### 8.5.3.5 Analysis of Immunogenicity Endpoints

Descriptive statistics of the immunogenicity assessment per treatment arm will be given with reference to the Safety Analysis Set unless otherwise specified in the SAP.

- Number and percentage of ADA positive patients at any time
- ADA titer
- Number and percentage of NAb positive patients
- Time to ADA
- Change of titer over time
- Persistent or transient ADA for patients with a treatment period  $\geq$  6 months

Presentations will include summaries of PK, safety, and efficacy endpoints over time for ADA positive and negative patients.

Correlation of PK, safety, and efficacy endpoints versus treatment group split by upper and lower quartile patients, based on their maximum ADA titer values, may be presented as exploratory analyses.

ADA status, titer, and NAb status will be listed and summarized by treatment and time point of collection.

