Planned trial and treatment duration per subject: The planned trial duration per subject is approximately 17 months: a screening period of 28 days to 3 days prior to IMP administration, a double-blind 48-week treatment period to evaluate long-term safety and immunogenicity, a safety follow-up visit four weeks after the last dose of IMP, and an additional safety evaluation at four months following the last dose of IMP. During the 4-week Safety Follow-up period, no excluded treatment for RA (as defined in the protocol) should be administered. Treatment for RA from the 4-week Safety Follow up visit to the 4-month Safety Evaluation visit will be at the discretion of the Investigator following institutional standard of care.

7 Sample Size/Randomization

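### The ADA titer groups for the Week 12 DAS28-ESR boxplots rest on two conflicting time windows, and ranking ADA-negatives as 0 within each arm can give the same quartile label different meanings by product

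*SAP*

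**What the plan says.** SAP 15.3.2.1 plans boxplots of DAS28-ESR change at Week 12 by ADA status and by lower and upper titer quartile. For these plots it says that "the ADA status or ADA titers will be the values for the treatment period".

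It then defines the quartiles in two consecutive sentences. The first takes the "highest ADA titer value from each subject for the period from baseline to Week 12" and adds that "subjects with ADA negative for the whole period will be assigned to a titer value of 0". The second says "ADA titers will be computed by splitting the subjects by treatment arm, taking their highest ADA titer values for the treatment period", followed by "arranging the values from smallest to largest and splitting into quartiles".

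SAP Section 6 describes "a double-blind 48-week treatment period to evaluate long-term safety and immunogenicity", so the treatment period is not the first 12 weeks.

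Protocol 8.5.3.5 provides for a display "split by upper and lower quartile patients, based on their maximum ADA titer values" as something that may be presented as exploratory. It fixes neither the time window nor whether cut-offs are common to both arms. The documents give no rule for tied titers and no expected ADA rate.

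**The concern.** There are three separate issues.

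- **Window.** Two programmers following the SAP could build different groups from the same data. Under the longer window, exposure is measured partly after the outcome it is meant to explain. Subjects with too little joint-count improvement are also taken off treatment from Week 24 (SAP Section 6). A maximum taken over time on treatment can therefore depend on response.
- **Zeros.** ADA-negative subjects are ranked together with positives. If there are enough of them, the lower quartile is no longer a low-titer group; it is the ADA-negative group, which the same figure already shows.
- **Arm-specific cut-offs.** Each arm is ranked on its own, so the upper group is defined relative to that arm. If ADA incidence or titers differ, the same label covers different titers on the two products.

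At stake is whether this figure can be read across arms. Protocol 5.2.1 wants immunogenicity related to PK, safety and efficacy as part of the biosimilarity evidence.

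**Working it through.** The documents state no figure for these groups, so there is none to reproduce.

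**Inputs from the documents:** 130 subjects per arm (SAP 7.1); negatives set to 0, ranking within arm, and the two windows (SAP 15.3.2.1); a 48-week treatment period (SAP Section 6); immunogenicity samples at Weeks 24 and 36 among others (Protocol Table 1).

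**Assumptions, not in the documents:** ADA-negative shares from 10% to 75%; titers among positives log2-normal with median 16 and SD 2 doublings, rounded to doubling dilutions; all 130 per arm contribute.

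**1. Windows.** Take a subject who is negative through Week 12 and first positive at Week 24. Under the first definition the titer is 0. Under the second the subject is positive and may fall in the upper group, although the DAS28-ESR value plotted was measured 24 − 12 = 12 weeks earlier. The window also decides who is set to 0. This step needs no assumption about ADA rates.

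**2. Lower cut-off.** With 130 ranked values, 0.25 × 130 = 32.5, so the lower cut-off is the 33rd value; 0.75 × 130 = 97.5, so the upper is the 98th. The lower cut-off is 0 once 33 or more are negative (33/130 = 25.4%), and the upper is 0 once 98 or more are (98/130 = 75.4%).

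| Assumed negative share | Zeros of 130 | Lower cut-off | At or below it | Upper cut-off |
|---|---|---|---|---|
| 10% | 13 | 4 | 40 | 32 |
| 20% | 26 | 2 | 37 | 32 |
| 25% | 32 | 1 | 36 | 32 |
| 30% | 39 | 0 | 39 | 32 |
| 50% | 65 | 0 | 65 | 16 |
| 70% | 91 | 0 | 91 | 4 |
| 75% | 98 | 0 | 98 | 0 |

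From 30% negative on, the group at or below the lower cut-off is exactly the ADA-negative group. A true quarter (about 32) would need an arbitrary choice among tied zeros.

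**3. What the upper group contains.** If a share π is positive, the arm's 75th percentile lies at percentile (0.75 − (1 − π))/π of the positive titers:

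- π = 0.30: 0.05/0.30 = 16.7%
- π = 0.40: 0.15/0.40 = 37.5%
- π = 0.50: 0.25/0.50 = 50%

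At 30% positive, the upper quartile therefore holds about five-sixths of all positives.

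**4. Between arms.** With identical titers among positives, only the negative share differs:

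| Negative share, arm A / arm B | Upper cut-off, arm A / arm B |
|---|---|
| 40% / 40% | 16 / 16 |
| 50% / 60% | 16 / 8 |
| 30% / 60% | 32 / 8 |
| 60% / 80% | 8 / 0 |

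**5. Check of the remedy (30% / 60% negative).** Pooling the arms but keeping negatives at 0 leaves the lower cut-off at 0 (upper 16), so pooling alone does not help. Among positives pooled over arms (91 and 52 subjects) the cut-offs are 8 and 32 for both. The lower group (8 or below) then has 37 and 21 subjects, and the upper group (32 or above) also has 37 and 21. Each is about 40% of its arm's positives (37/91 = 41%, 21/52 = 40%) because doubling dilutions tie heavily, so a tie rule is still needed.

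**The case against.** The sentence that defines the quartiles already ends its window at Week 12, the visit of the plotted outcome, and the later phrase could be shorthand for that window. Within-arm quartiles are a legitimate way to look at titer and response inside one product, and the protocol does not require common cut-offs. Titer arises after randomization, so pooled cut-offs would not make the comparison a randomized one. The split is optional and exploratory in the protocol and carries no test or margin.

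Most of this stands and limits the weight of the point. The shorthand reading does not settle the window, because the SAP uses the term elsewhere for 48 weeks and uses it twice in this section.

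A reader might also infer three stronger things that the documents do not support:

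- **That the lower quartile is undefined.** The cut-off always exists, at worst as 0. What is missing is a rule for ties, and whether ties matter depends on an ADA rate that is not given.
- **That a titer difference between the products would be hidden.** SAP 15.3.2 plans titer summaries by arm and visit, titer boxplots, and ADA and NAb positivity by visit.
- **That response cannot be compared at like titers anywhere in the report.** SAP 15.3.2.1 also plans scatterplots of percentage change in DAS28-ESR, CDAI and SDAI against titer for each treatment, without cut-offs.

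**Conclusion.** The point holds as a minor one. The conflict between the two windows is in the text, needs no assumption, and must be reconciled.

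The grouping problem is conditional. The lower group repeats the ADA-negative group if more than 25% of an arm is negative over the window used. The upper labels differ in meaning if the arms differ in ADA rate or in titers; with equal rates and titers the cut-offs coincide. The cut-offs of 32 and 8 illustrate an assumed titer distribution and are not a forecast.

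The effect is confined to how one exploratory figure can be read across arms. The primary endpoint, the ACR20 analysis at Week 12 and the sample size are untouched.

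**What to change.** Replace the two quartile sentences in SAP 15.3.2.1 with one rule:

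- Use each subject's highest titer from baseline up to the visit at which efficacy is measured, here Week 12. Use the same window for ADA status in this figure.
- Show subjects who are ADA-negative over that window as a separate group, not ranked as 0.
- Split ADA-positive subjects at cut-offs computed from both arms together: quartiles, or the median if positives are few.
- State to which group a titer equal to a cut-off belongs.

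The cost is a few sentences and no new data. Group sizes will differ between arms and may be small: with 60% and 80% negative in the illustration above, the upper groups would hold 21 and 10 subjects. The change should be made before unblinding, since SAP Section 5 requires unplanned analyses to be identified as such in the study report.

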15.3.3 Pharmacokinetic Analysis

15.3.3.1 Serum Concentrations of Adalimumab

All PK analysis will be performed using the PK analysis set (see Section 10.2).

All subjects will have PK samples taken pre-first dose, and then prior to dosing on Weeks 2, 4, 12, 24, 36, and 52. In addition, a subset of 60 subjects (30 per arm) will have additional samples to support the population PK analysis taken on Days 2 (24 h post first dose), 4, and 9, and Days 2 (24 h post Week 24 dose), 4, 9, and 14 (Week 26 pre-dose) after the Week 24 dose.

A listing of nominal and actual PK blood sample collection times as well as the derived sampling time deviations (as applicable) will be provided for all subjects.

Concentrations for adalimumab will be listed and summarized by treatment arm and visit using descriptive statistics for the subset of 60 subjects (30 per arm) with additional samples taken on the following timepoints: Week 0: Day 1 pre-dose, Days 2 (24 h post first dose), 4, and 9, and 14 (Week 2 pre-dose); Week 24: Day 1 pre-dose, Days 2 (24 h post Week 24 dose), 4, 9, and 14 (Week 26 pre-dose).

In order to facilitate direct evaluation of adalimumab trough serum concentrations across visits, an additional presentation of adalimumab data with summary statistics will be produced for trough samples at visits Week 0, 2, 4, 12, 24, 26, 36, 52.

Below the lower limit of quantitation (< LLOQ) concentrations will be treated as zero for the computation of descriptive statistics. Missing concentrations will be omitted from the calculation of descriptive statistics. Missing PK concentrations (eg no sample, insufficient sample volume for analysis, no result or result not valid) should be reported generally as "N.R.".

Pharmacokinetic concentrations will be summarized using descriptive statistics, including number of non-missing observations (n), mean, SD, coefficient of variation (CV%), minimum, median, and maximum. The geometric mean and geometric coefficient of variation will also be reported for visits where there are no concentrations below the limit of quantitation. The following conventions will be applied when reporting descriptive statistics of PK concentration data: mean, geometric mean, minimum, median, and maximum will be presented with 3 significant digits; SD 4 significant digits; CV% and geometric CV% 1 decimal place.

Figures of mean concentration-time data for trough adalimumab serum concentrations will be presented on linear (\pm SD) and semi logarithmic scales by treatment arm, and with treatments overlaid together as appropriate. Individual and mean trough adalimumab concentration-time data by treatment arm and visit week will be graphically presented on linear scale.

Concentrations for adalimumab will be listed and summarized by treatment arm and by ADA status (positive/negative) to assess the correlation between PK and ADA data. Also, a figure of mean (\pm SD) concentration-time data for adalimumab samples by ADA status (positive/negative) on linear scale will be presented by treatment arm, as appropriate.

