a For patients who do not achieve a reduction in both swollen and tender joints of ≥ 20% at Week 24 or at any other later-scheduled time point, the IMP will be discontinued. These patients will remain in the trial safety analysis set and participate in the safety and immunogenicity assessments.

b The treatment termination information must be recorded during the Week 52 visit and the ET visit, and trial termination information must be recorded during the Safety Follow-up visit.

c Patients who discontinue from treatment will immediately have an ET visit and return for a safety follow-up visit 4 weeks after the last dose of IMP. Patients will return for an additional safety evaluation 4 months after the last dose of IMP. The 4-week and 4-month Safety Follow-up visits will not be duplicated if either of these visits falls within 2 weeks of an otherwise scheduled visit. If the 4-week and 4-month Safety Follow-up since last IMP are completed within the 52 week visit schedule, these will not be repeated thereafter.

d Medical history must include the following: disease phenotype, disease duration, infectious complications, disease localization, previous treatment(s) including identification of any previous biologic and nonbiologic RA therapy or history of treatment for latent or active TB, previous surgery/surgeries and smoking status.

e Review & update medical history only, to ensure patient remains qualified for the study.

f Screening results should be re-checked (particularly virus serology and TB tests) to ensure that the patient remains eligible for the trial.

g IMP will be administered every other week. During weeks with scheduled trial site visits, IMP will be administered at the site. During all other weeks, the patient (or a caregiver) will self-inject/inject IMP at home. Patients must be monitored for 1 hour following IMP administration on Day 1 of Week 0, Week 2, and Week 4. Last dose of IMP will be at Week 48.

h Height will be measured at screening only.

i Follicle-stimulating hormone test will be performed to confirm postmenopausal status of women with continuous amenorrhea ≥ 12 months.

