## 6.2

### Dosage and Administration

MSB11022-CCI [REDACTED] will be administered at a dose of 40 mg s.c. every other week starting from baseline up to and including Week 48.

The Humira® will be administered at a dose of 40 mg s.c. every other week starting from baseline up to and including Week 48.

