## 7.5 Pharmacokinetics

The timing of sampling for PK analysis is based on available steady-state data from RA patients treated with 40 mg adalimumab s.c. These data showed that adalimumab steady-state concentrations were reached approximately 20 weeks after the beginning of adalimumab treatment ([60, 61](#)). Sparse sampling for population PK analysis will be collected in a subset of patients (at least 30/arm) in this trial.

All patients will have PK samples taken pre-first dose, and then prior to dosing on Weeks 2, 4, 12, 24, 36, and 52. In addition, a subset of 60 patients (30 per arm) will have additional samples to support the population PK analysis taken on Days 2 (24 h post first dose), 4, and 9, and Days 2 (24 h post Week 24 dose), 4, 9, and 14 (Week 26 pre-dose) after the Week 24 dose (see [Table 2](#)).

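### The Week 52 adalimumab sample is summarised as a trough although dosing ends at Week 48, so a level 28 days after the last dose sits among 14-day troughs

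*SAP*

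**What the plan says.** Protocol Section 6.2 has each product "administered at a dose of 40 mg s.c. every other week starting from baseline up to and including Week 48". Footnote g to the Schedule of Assessments (Protocol Table 1) agrees: "Last dose of IMP will be at Week 48".

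The PK sampling text reads differently. SAP Section 15.3.3.1 says: "All subjects will have PK samples taken pre-first dose, and then prior to dosing on Weeks 2, 4, 12, 24, 36, and 52". SAP Section 6 has the same schedule, as do the protocol synopsis and Protocol Sections 5.2 and 7.5, where samples are taken "prior to dosing on Weeks 2, 4, 12, 24, 36, and 52". Footnote r to Protocol Table 1 likewise assumes that product is given on site at every visit with a PK sample.

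SAP Section 15.3.3.1 then adds a table with a stated purpose, "In order to facilitate direct evaluation of adalimumab trough serum concentrations across visits", and fills it with "trough samples at visits Week 0, 2, 4, 12, 24, 26, 36, 52". It goes on to plan "Figures of mean concentration-time data for trough adalimumab serum concentrations" by arm, without listing the visits to be plotted. Concentrations by ADA status follow.

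The trough endpoint itself (Protocol Section 8.3.3, SAP Section 6) ends with the sample taken 14 days after the Week 24 dose. Week 52 is not part of it.

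**The concern.** A trough is the level just before the next dose. On the dosing sections as they stand, no dose is due at Week 52, so the sample cannot be pre-dose, and the interval since the last dose is not that of the other visits. A table meant for comparing troughs across visits needs the same interval at each of them.

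At stake is how the last point of the exposure profile is read. A reader of the table, or of a trough curve ending at Week 52, would see concentrations drop at the final visit and could take this for a loss of exposure late in treatment. The same sample also enters the summaries by ADA status, where a late drop invites an immunogenic explanation.

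Nothing else in the plan corrects this. SAP Section 11.1 presents data by nominal visit without windowing. The listing of sampling-time deviations compares actual with nominal times, but here the nominal label is itself the problem. The events affecting PK quality named in SAP Section 10.2.5 do not include time since last dose.

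**Working it through.** **Inputs.** Dosing every 2 weeks from Week 0 to Week 48 (Protocol Section 6.2), which is 48/2 + 1 = 25 planned doses. Trough visits: Weeks 0, 2, 4, 12, 24, 26, 36 and 52 (SAP Section 15.3.3.1). Visit window: ±2 days (Protocol Table 1 and Section 7.1.2).

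**Step 1: the plan's own trough interval.** SAP Section 15.3.3.1 equates the Week 26 pre-dose sample with Day 14 after the Week 24 dose. Check: (26 − 24) × 7 = 14 days. It reproduces.

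**Step 2: the same sum for every listed visit.** Interval = 7 × (sample week − week of the last planned dose before it).

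| Sample | Last planned dose before it | Interval | Dose due at this visit? |
|---|---|---|---|
| Week 0 | none | none | yes (first dose) |
| Week 2 | Week 0 | 14 days | yes |
| Week 4 | Week 2 | 14 days | yes |
| Week 12 | Week 10 | 14 days | yes |
| Week 24 | Week 22 | 14 days | yes |
| Week 26 | Week 24 | 14 days | yes |
| Week 36 | Week 34 | 14 days | yes |
| Week 52 | Week 48 | 28 days | no |

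**Step 3: visit windows.** If the Week 48 and Week 52 visits both move by up to 2 days, the last interval runs from 28 − 4 = 24 to 28 + 4 = 32 days. The same allowance on a 14-day interval gives 14 − 4 = 10 to 14 + 4 = 18 days. The ranges do not overlap.

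**Step 4: size.** The documents give no half-life, so it is assumed here. With first-order decline, the level at Day 28 divided by the level at Day 14 after the same dose is 2^(−14/half-life).

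| Assumed half-life | Week 52 value as a share of a 14-day trough | Apparent fall |
|---|---|---|
| 10 days | 2^(−1.4) = 0.379 | 62% |
| 14 days | 2^(−1) = 0.500 | 50% |
| 20 days | 2^(−0.7) = 0.616 | 38% |
| 28 days | 2^(−0.5) = 0.707 | 29% |

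The natural visits to compare with Week 52 are Weeks 24, 26 and 36, because Protocol Section 7.5 puts steady state at about 20 weeks. Against those, the fall above comes from timing alone.

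**The case against.** Much can be said for a narrow reading, and most of it stands.

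- **Comparison between arms.** A reader might infer that the comparison of MSB11022 with Humira is biased. The documents do not support that. Both arms follow the same schedule, so Week 52 is like for like between them.
- **Endpoint.** The trough endpoint omits Week 52. The table is an additional descriptive display, and population PK has its own analysis plan (SAP Section 15.4.1).
- **ADA subgroups.** A reader might infer that ADA-positive patients are distorted most. That does not follow. Take a bolus model at steady state with r = 2^(−14/half-life), in units of dose over volume. The 14-day trough is r/(1 − r), the Day 28 level is r²/(1 − r), and the difference is r. For assumed half-lives of 14 and 7 days the absolute falls are 0.50 and 0.25, while the proportional falls (1 − r) are 50% and 75%. Faster clearance gives a larger proportional fall but a smaller absolute one, and the planned figure by ADA status is on a linear scale. No claim is made here about which subgroup is affected most.
- **Labelling.** The SAP does not write 14 days beside Week 52, and SAP Sections 16.3 to 16.5 pair the Week 52 visit with the 4-week safety follow-up. This makes a misreading less likely. It does not change a PK section that calls the sample pre-dose and groups it with troughs.
- **Figures.** Their visits are not listed. That Week 52 is plotted is an inference from the table.
- **Other differences between visits.** Weeks 2, 4 and 12 precede steady state, so some change across visits is expected anyway. Patients taken off treatment who still give samples could exceed 14 days at Week 36 too. Removing Week 52 does not settle that case.
- **Week 0.** Patients must be adalimumab-naïve, so a pre-dose value there misleads few readers. The point is mainly one of presentation.

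**Conclusion.** The concern holds as an error of classification in a descriptive display. On the dosing text, the Week 52 sample of an on-schedule patient is 28 days after the last dose (24 to 32 with windows), twice the nominal interval of every other post-dose visit in the table. Following the SAP as written would report about 38% to 62% of a 14-day trough as the Week 52 trough, for assumed half-lives of 10 to 20 days and first-order decline. That the interval is twice as long does not depend on the assumed half-life; the percentages do.

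The concentrations themselves would be correct measurements of decline after dosing ends. What is wrong is the trough label and the across-visit reading that it invites. The effect extends to the trough-over-time figures only if they use the same visits as the table.

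**What to change.** In SAP Section 15.3.3.1:

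- limit the trough table and trough figures to Weeks 2, 4, 12, 24, 26 and 36, and state the visits for the figures;
- report Week 52 separately as *4 weeks after last dose*, and label it that way in any display of concentration by ADA status;
- show Week 0 as the pre-dose baseline.

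Reconcile the text that describes Week 52 as a pre-dose sample with the text that places the last dose at Week 48. The sampling wording stands in the protocol synopsis, Protocol Sections 5.2 and 7.5, and SAP Sections 6 and 15.3.3.1. Footnote r to Protocol Table 1 carries the same assumption.

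The cost is SAP text and table and figure shells, plus a minor protocol clarification documented under Protocol Section 10.5. No sample, visit or measurement changes, and the Week 52 data are kept.
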